1.2 Changes from previous version of SAP

A summary of key changes from earlier versions of SAP, with particular relevance to protocol changes that have an impact on the design, definition, sample size, data quality/collection and analysis of the outcomes will be provided. Include protocol version number and date.

Version number Issue date	Author of this issue	Protocol Version & Issue date	Significant changes from previous version together with reasons
V1.0_10Jul2018	[name] [name]	Protocol_V4.0_14May2018	Not applicable as this is the 1 st issue
V2.0_07Jan2021	[name] [name]	Protocol_V5.0_26Oct2020	
 • Updated to be based on V5.0 of the protocol • Simulation results moved to an Appendix 1 Document • Reference made to Protocol Decision Point Plan and clarification of dose decisions • Change in TiTE CRM's weight function • Change in sensitivity analyses presented at each dose decision • Removal of references to Stage B

Note: All references to Stage B's dose allocation methods have been removed from V2.0 of this Analysis Plan. This is to facilitate dose decisions for Stages A1 and A2 to be based on a finalised SAP while the analysis methods for the redesigned Stage B in V5.0 of the protocol are being considered. This Analysis Plan will be updated to include Stage B's planned analysis methods prior to Stage B opening to recruitment.

A phase I dose escalation safety study combining the ATR inhibitor VX-970 with chemoradiotherapy in oesophageal cancer using time to event continual reassessment method (funded by CRUK and Merck)
EudraCT Number: 2015-003965-27

2. BACKGROUND AND OBJECTIVES

2.1 Background and rationale

This phase I study will test the combination of a novel ATR inhibitor (M6620) with chemoradiotherapy in oesophageal cancer. In the first two cohorts (Stage A1 and A2), we will investigate the safety of combining M6620 separately with [1] palliative radiotherapy (RT) for oesophageal cancer (Stage A1) and [2] with cisplatin/capecitabine chemotherapy in patients with advanced inoperable and metastatic solid tumours (Stage A2). In Stage A1, M6620 will be given in combination with high dose palliative RT treatment, aiming to deliver M6620 twice weekly during RT escalating to a dose of 240mg/m². A palliative chemotherapy cohort (Stage A2) will open to recruitment simultaneously where M6620 will be given in combination with cisplatin/capecitabine chemotherapy, aiming to deliver M6620 twice weekly escalating to a dose of 140mg/m² twice weekly. When we have enough information to suggest the combinations are tolerable, the ATR inhibitor will be tested in the definitive setting (Stage B) in combination with cisplatin/capecitabine and radical RT to identify the MTD. The MTD found in this study will be taken forward in future phase II studies.

In the palliative setting, we aim to find the schedule associated with no more than 25% Dose Limiting Toxicities (DLTs) in stage A1 on the basis that palliative oesophageal radiotherapy causes approximately 20% grade 3 and 4 toxicity, and 30% Dose Limiting Toxicities (DLTs) in stage A2 are derived from capecitabine/cisplatin used in the radical setting (SCOPE1 study).

In the radical setting, we aim to find the schedule associated with no more than 45% DLTs on the basis that conventional oesophageal chemoradiation causes a grade 3 and 4 toxic event rate of 28% haematological toxicity and 63% non-haematological toxicity of which 34% is gastrointestinal as reported in the standard arm of SCOPE1 study (12). Comparable toxicity rates were described in the standard arm of the PRODIGE5/ACCORD17 study: grade 3 and 4 neutropenia 29% and grade 3 and 4 dysphagia and oesophagitis 33%.

The trial will find the best optimal dose and dosing schedule using the TiTE-CRM (Time To Event Continual Reassessment Method). The CRM is a model based method for finding the MTD. It assumes that toxicity increases monotonically with increasing dose, and that efficacy also increases with increasing dose. The aim will be to find the dose that causes a DLT with the above specified target toxicity levels. TiTE-CRM is a modified CRM that accounts for the time to event of late onset toxicities. The advantages of a TiTE-CRM are that all current information is used when deciding which dose to give the next patient and it is not necessary for a patient to complete the full observation period before consenting the next patient. This results in a better estimation of the MTD and shorter study duration respectively.

A phase I dose escalation safety study combining the ATR inhibitor VX-970 with chemoradiotherapy in oesophageal cancer using time to event continual reassessment method (funded by CRUK and Merck)
EudraCT Number: 2015-003965-27

2.2 Objectives

Stage A1		
Primary Objective	Endpoints/ Outcome Measures	Time point(s) for evaluation of end point

 To determine the best tolerated M6620 treatment schedule (or phase II recommended dose (RPTD)) administered concomitantly with Radiotherapy only in the palliative treatment of oesophageal cancer 	Highest treatment schedule resulting in less than 25% dose limiting toxicity (DLT) rate (see section 9.1.2 for DLT definitions)	
 Week 9
Secondary Objectives	Endpoints/ Outcome Measures	

 To determine the safety and toxicity profile of M6620 administered concomitantly with RT only in the palliative treatment of oesophageal cancer 	
 Any toxicity grade ≥ 3 graded according to CTCAE v4.03 and length of time for toxicity to resolve 	
 During radiotherapy Weeks 1-3 Week 4, 9 and week 12

 To determine if M6620 can be delivered in combination with palliative RT 	
 Proportion of patients completing at least 75%, 90% and 100% of the planned RT dose 	
 End of radiotherapy End of Week 3

 Efficacy of the combination 	
 Objective tumour response (OR) as evaluated by CT scan and quantified by Response Criteria Evaluation (RECIST 1.1) PFS and OS from D1 In field radiotherapy control 	
 12 weeks 6 and 12 months
Stage A2		
Primary Objective	Endpoints/ Outcome Measures	Time point(s) for evaluation of end point

 To determine the best tolerated M6620 treatment schedule (or phase II recommended dose (RPTD)) administered concomitantly with chemotherapy (Cisplatin and Capecitabine) only in the palliative treatment of solid cancer 	
 Highest treatment schedule resulting in less than 30% dose limiting toxicity (DLT) rate (see section 9.1.2 for DLT definitions) 	
 Week 4
Secondary Objectives	Endpoints/ Outcome Measures	

 To determine the safety and toxicity profile of M6620 administered concomitantly with chemotherapy (Cisplatin and Capecitabine) only in the palliative treatment of solid cancer 	
 Any toxicity grade ≥ 3 graded according to CTCAE v4.03 and length of time for toxicity to resolve 	
 During chemotherapy Week 1-18 Week 20, 26

A phase I dose escalation safety study combining the ATR inhibitor VX-970 with chemoradiotherapy in oesophageal cancer using time to event continual reassessment method (funded by CRUK and Merck)
 EudraCT Number: 2015-003965-27

 To determine if M6620 can be delivered in combination with palliative chemotherapy Efficacy of the combination 	
 Proportion of patients completing at least 75%, 90% and 100% of the planned dose Objective tumour response (OR) as evaluated by CT scan and quantified by Response Criteria Evaluation (RECIST 1.1) PFS and OS from D1 	
 End of chemotherapy Week 18 Week 6, 12, 18, 26 Week 26 & 12 months
Tertiary Objectives	Endpoints/ Outcome Measures	

 To evaluate pharmacokinetics (PK) of M6620 when administered in combination with Cisplatin and Capecitabine 	
 M6620 C_{max} (observed peak plasma concentration) and AUC (area under the plasma concentration time curve) using blood samples when delivered after Capecitabine and Cisplatin administration 	
 1st dose of M6620 (C1D2) at the following timepoints: BOI, at 0.5 hours before EOI, at EOI and at 0.5, 1, 2, 3, 6, 23, 47 hours after EOI. For C1D9 and C1D16 doses at the following timepoints: BOI and EOI

Stage B		
Primary Objective	Endpoints/ Outcome measures	Time point(s) for evaluation of end point

 To determine the best tolerated M6620 treatment schedule (or phase II recommended dose (RPTD)) administered concomitantly with radiotherapy (dCRT) in combination with cisplatin and capecitabine in the radical treatment of oesophageal cancer 	Highest treatment schedule resulting in less than 45% dose limiting toxicity (DLT) rate (see section 9.1.2 for DLT definitions)	
 Up to Week 24
Secondary Objectives	Endpoints/ Outcome Measures	

 To determine the safety and toxicity profile of M6620 administered concomitantly with dCRT in combination with cisplatin and capecitabine in the radical treatment of oesophageal cancer 	
 Any toxicity grade ≥ 3 graded according to CTCAE v4.03 and length of time for toxicity to resolve 	
 Up to week 24

 To determine tolerance and ability to deliver M6620 in combination with standard dCRT 	
 Treatment tolerance and deliverability measured by proportion of patients completing at least 80% of the planned chemotherapy dose and at least 20 fractions of RT 	
 End of induction chemotherapy and dCRT. End of week 11

 Efficacy and long term safety of the combination 	
 Objective tumour response (OR) as evaluated by CT scan and quantified by 	
 24 weeks

	Response Criteria Evaluation (RECIST 1.1) and endoscopic and biopsy findings. • PFS and OS from D1	
Tertiary/Exploratory Objectives	Endpoints/ Outcome Measures	
• To explore target effects in tissue	• Change in level of ATR inhibition and apoptosis in M6620 treated tissue using IHC. • Genotyping of tumours • Aim to identify markers for oesophageal cancer in the blood	• Biopsies at baseline, week 7 and 24 • Blood samples at baseline, week 7 and week 12

3. STUDY METHODS

3.1 Trial Design/framework

This will be a single arm, open-label, phase I dose escalation trial using the Time-To-Event Continual Reassessment Method (TiTE-CRM) to find the optimal treatment schedule. The trial consists of three stages A1, A2 and B. Stages A1 and A2 will run concurrently and will inform the starting dose of M6620 for Stage B.

3.1.1 General description of the TiTE-CRM design

The TiTE-CRM method is a modified version of the CRM that accounts for late-onset toxicities. It uses all current information when deciding which dose to give the next patient and it is not necessary for a patient to complete the full observation period before consenting the next patient. This results in a better estimation of the MTD and shorter study duration respectively and is particularly useful in trials involving radiotherapy where the toxicity follow-up phase is longer. We assume that:

- A maximum of N subjects are to be recruited
- A target toxicity level, TTL
- K doses d_1, \dots, d_K to be explored
- A DLT window of length T
- The maximum amount of dose of M6620 for the patient's allocated treatment schedule D
- A weight function, w , associated with T and D denoting a combination of the proportion of the DLT window that has been observed and proportion of the total M6620 they're to receive for each currently enrolled patient
- Prior estimates of DLTs at each dose, also called the skeleton, $\hat{\pi}_0 = \{\hat{\pi}_{01}, \dots, \hat{\pi}_{0K}\}$
- Dose toxicity curve (DTC), $g_k(\alpha) = d_k^{\exp \alpha}$
- Prior distribution for the parameter of the DTC, $\alpha \sim N(0, \sigma^2)$

A phase I dose escalation safety study combining the ATR inhibitor VX-970 with chemoradiotherapy in oesophageal cancer using time to event continual reassessment method (funded by CRUK and Merck)
 EudraCT Number: 2015-003965-27

At the start of the trial the information on the probability of DLT at each dose level is given by the prior estimates $\hat{\pi}_0$. These estimates are updated after every patient to give the posterior estimates.

Suppose there are J subjects currently enrolled, the available information is the set of doses $\{x_1, \dots, x_J\}$ administered to the J patients, the set of toxicity outcomes $\{y_1, \dots, y_J\}$ where $y_j = 0$ if no toxicity and $y_j = 1$ if toxicity, and the amount of time each patient has been observed $\{u_1, \dots, u_J\}$, where $0 \leq u_j \leq T$. The amount of M6620 given per dose schedule $\{v_1, \dots, v_J\}$, where $0 \leq v_j \leq D$.

The TiTE-CRM model uses a weighted likelihood function given by

$$L(\alpha) = \prod_{j=1}^J \left[g_{x_j}(\alpha) * w_j \right]^{y_j} \left[1 - g_{x_j}(\alpha) * w_j \right]^{1-y_j}$$

where

$$w_j = \begin{cases} 1 & \text{if } y_j = 1 \\ \frac{1}{2} \left(\frac{u_j}{T} + \frac{v_j}{D} \right) & \text{if } y_j = 0 \end{cases}$$

[figure not shown]
and the posterior expected toxicity at each dose (posterior dose-toxicity curve) is given by

$$\hat{\pi}_k = E(g_k(\alpha)|y) = \int_{-\infty}^{\infty} g_k(\alpha) p(\alpha|y) d\alpha$$

The MTD is defined to be the dose x^* such that $\hat{\pi}_k = TTL$. As each new patient is enrolled, the current best guess at the MTD is calculated based on all data accrued so far, and is the dose suggested for the patient in agreement with the TMG.

In addition the trial may be stopped early if either the drug is found to be too toxic or we are confident in our estimate of the MTD. The flow of patients through a CRM trial is given in Figure 1.

Figure 1: Flow of patients through a CRM trial

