Physical Exam ⁶	X		X	X	X	X	X	X	X	X	X	X	X	X	X	X
Weight ⁶	X		X	X	X	X	X	X	X	X	X	X	X	X	X	X
Vital signs	X								X ⁸							
ECG ⁷	X		X			X			X			X				
Audiogram monitoring ¹³		X				X										
Concurrent medications ⁶	X		X	X	X	X	X	X	X	X	X	X	X	X	X	X
DLT Assessment ⁶			X	X	X	X										
AE Assessment ⁶			X	X	X	X	X	X	X	X	X	X	X	X	X	X
CT chest abdomen pelvis ⁹	X							X						X		X

¹ Screening assessments including: pregnancy test (to be repeated for WOCBP 4 weekly during treatment), height and medical history, see section 5.3

² Capecitabine taken bd weeks 1 to 18

³ Cisplatin given on day 1 (Mon)

⁴ M6620 (Berzosertib) given on day 2 only (Tues) dose schedules 1 & 3; M6620 (Berzosertib) given on day 2 & day 5 (Tues/Fri) dose schedules 2 & 4

⁵ Check Haem/Biochem within 72 hours prior to cisplatin and 24 hours preceding M6620 (Berzosertib) (only one sample needs to be taken if it satisfies both Cisplatin and M6620 (Berzosertib) requirements): Hb, ANC, lymphocytes, WBC, Platelets, Bilirubin, ALP, AST or ALT, Serum creatinine, Urea, K⁺, Na⁺, eGFR, Ca, Mg, Phosphate

M6620 (Berzosertib) M6620 (Berzosertib)⁶ Assessment done within 24 hours prior to M6620 (Berzosertib) dosing (weight once weekly)

⁷ ECG to be carried out at screening, pre-treatment and once per cycle

⁸ Per clinical requirement

⁹ CT chest abdomen pelvis in weeks 6, 12, 18 and at 8 weeks post EOT. Screening CT only needs to be done if staging CT was carried out > 35 days prior to start of treatment.

¹⁰ Patients can continue with treatment after 4 cycles if CT shows no progression and at the discretion of the PI.

¹¹ Two week follow-up should be 2 weeks after last dose (+/- 7 days); 8 week follow-up should be 8 weeks after last dose (+/- 2 weeks)

¹² If required.

*Each cycle lasts 3 weeks

Repeat assessments
done for cycles 3-4 in
cycles 5-6 (if
applicable)

SUMMARY SCHEDULE OF EVENTS STAGE B

¹Screening assessments including: pregnancy test (to be repeated for WOCBP 4 weekly during treatment), height, medical history, Echo/MUGA and Lung function test, see section 5.3

² Capecitabine taken bd weeks 1 to 6; capecitabine taken bd Mon to Fri weeks 7 to 11

³ Check Haem/Biochem within 72 hours prior to cisplatin and 24 hours preceding M6620 (Berzosertib) (only one sample needs to be taken if it satisfies both Cisplatin and M6620 (Berzosertib) requirements): Hb, ANC, lymphocytes, WBC, Platelets, Bilirubin, ALP, AST or ALT, Serum creatinine, Urea, K⁺, Na⁺, eGFR, Ca, Mg, Phosphate

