9.3.1 Additional guidance Stage A2

In stage A2 M6620 (Berzosertib) must not be dose reduced in the first 4 weeks of treatment but doses may be omitted for toxicity (as above). The M6620 (Berzosertib) dose may be reduced after the 4 week DLT window is complete as follows:

1. For Grade 4 hematologic toxicity: dose of M6620 (Berzosertib) to be reduced by 25%.
2. For Grade 3 non-hematologic toxicity: dose of M6620 (Berzosertib) to be reduced by 25%.
3. For Grade 4 non-hematologic toxicity: dose of M6620 (Berzosertib) to be reduced by 50%.

If the dose of M6620 (Berzosertib) has already been reduced by 25% a further dose reduction of 25% may be made to 50% of starting dose. However no further dose reductions may be made beyond 50% of starting dose and the patient should come off study if further Grade 3 or 4 non-haematologic toxicity or Grade 4 haematologic toxicity is then experienced.

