3.1.2 Stage A2

The aim is to find the M6620 treatment schedule when combined with palliative combination chemotherapy (Cisplatin and Capecitabine) that is associated with no more than a 30% dose limiting toxicity rate. Four treatment schedules are proposed. Each schedule comprises a specific combination of dose and dosing frequency. There are two possible M6620 doses and two dosing frequencies (see section 4.2.1). Chemotherapy dose remains consistent across all treatment schedules. For the prior estimates of DLT at each treatment schedule see the skeleton in Table 1.

The treatment involves six cycles of chemotherapy with three weekly Cisplatin and Capecitabine and M6620 at a pre-determined frequency dependent on the treatment schedule allocated to the individual patient. The follow-up of a further 8 weeks provides a total observation window of 26 weeks. DLT assessments will be carried out during the first 4 weeks of treatment. The MTD will be determined during this period using the TiTE-CRM. An initial cohort of three patients will receive the starting schedule (lowest dosing frequency) at the starting dose. The fourth patient will not be recruited until all three patients have been followed for a minimum of 4 weeks from the start of chemotherapy or until the occurrence of a DLT.

From the fourth patient, all eligible patients will be continuously recruited and the TiTE-CRM will be used to assign their treatment schedule. To ensure enough information is accumulated to inform the assignment of the treatment schedule to the subsequent patient, recruitment will be managed by allocating treatment slots (see Protocol section 4.4 for further details).

Stage A2 stopping rules

Stage A2 will stop for safety if, at any point in the trial, there is sufficient evidence to suggest that schedule 1 is too toxic. More specifically, we will consider schedule 1 to be too toxic if, given all the available data, there is a high probability that the DLT rate is greater than the target toxicity level of 0.3. If the first three patients recruited to Stage A2 have DLTs at treatment schedule 1, then the starting schedule (treatment schedule 1) will be deemed too toxic and the trial will stop.

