4.2 Stage A2 Treatment

Two dose levels and 2 dosing frequencies (treatment schedules) are proposed. Both the dose and frequency of M6620 will vary but the Cisplatin and Capecitabine dose and schedule will remain unchanged across treatment plans. The treatment schedule will last for 6 cycles (18 weeks).

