4.2.1 M6620 Treatment Schedule – Stage A2

The starting dose of M6620 will be 90mg/m² IV once weekly (schedule 1). For all schedules, see Table 3. The treatment schedule of M6620 will be escalated or de-escalated using the TiTE-CRM model.

Table 3: Stage A2 - Dose Escalation Schedule

Dose Escalation schedule	
Treatment schedule	Dose of M6620 and days of the schedule it will be delivered
1	90 mg/m ² once a week for 18 weeks (Tuesdays)
2	90 mg/m ² twice a week for 18 weeks (Tuesdays and Fridays)
3	140 mg/m ² once a week for 18 weeks (Tuesdays)
4	140 mg/m ² twice a week for 18 weeks (Tuesdays and Fridays)

*Doses are stated as exact dose in units. No intermediate dose levels or further splitting of the dose allowed

A phase I dose escalation safety study combining the ATR inhibitor VX-970 with chemoradiotherapy in oesophageal cancer using time to event continual reassessment method (funded by CRUK and Merck)
 EudraCT Number: 2015-003965-27

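### The Stage A2 TiTE-CRM weight divides M6620 received by the 18-week schedule total although the DLT window is 4 weeks, so completed DLT-free observations are under-counted

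*SAP*

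**What the plan says.** SAP 3.1.1 gives a patient with a DLT weight 1 and a patient without one w = ½(u/T + v/D). Here u is time observed, T the DLT window, v the M6620 given, and D the maximum M6620 for the patient's "allocated treatment schedule D". In words, the weight is described as "denoting a combination of the proportion of the DLT window that has been observed and proportion of the total M6620" the patient is to receive. The definition is general, and no value of D is given by stage.

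For Stage A2, SAP 3.1.2 states: "DLT assessments will be carried out during the first 4 weeks of treatment". It adds: "The MTD will be determined during this period using the TiTE-CRM". Table 1 confirms the 4-week window. The dosing is much longer. SAP 4.2 says "The treatment schedule will last for 6 cycles (18 weeks"), and Table 3 gives schedules 1 and 3 "once a week for 18 weeks (Tuesdays") and schedules 2 and 4 twice a week over the same 18 weeks.

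Two Protocol provisions affect how much of the 18-week total is received. The Stage A2 schedule of events says: "Patients can continue with treatment after 4 cycles if CT shows no progression and at the discretion of the PI". Section 9.3.1 says the M6620 "dose may be reduced after the 4 week DLT window is complete as follows".

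**The concern.** The A2 endpoint is a DLT within 4 weeks. When the window closes without a DLT, that outcome is fully known. Under the written weight, the observation still counts as incomplete, and how much it counts depends on M6620 given, withheld or reduced in weeks 5 to 18. That does not fit the statement that the MTD is determined within the first 4 weeks.

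Stage A1 does not have the problem. Its last M6620 dose is on day 16 or 19 of a 9-week window, so a fully dosed DLT-free patient reaches w = 1 when the window closes. The general formula suits A1 but does not carry over to A2.

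DLTs count in full and completed DLT-free windows are discounted, so the estimated DLT rate is too high. The weights feed every A2 allocation, the 0.95 safety rule and the A2 MTD. They also bear on when Stage B may open, because one of its starting rules depends on how many A2 patients have reached schedules 3 and 4.

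**Working it through.** **Inputs.** From the SAP: w = ½(u/T + v/D), T = 4 weeks, D = 18 weekly (or 36 twice-weekly) doses, target 0.30, skeleton 0.17/0.20/0.25/0.30, power curve g = d^exp(α) with α ~ N(0, 1.158²), first cohort of 3, one patient every 3 weeks, no skipping when escalating, stop at 6 on schedule 4 or 20 in total, safety stop at posterior probability above 0.95.

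**The plan's own figure.** SAP 3.6 gives an A2 sample size of 16 (11, 20). The simulation scenarios are not in the documents, so I assumed that the truth equals the skeleton and that DLT times are uniform over 4 weeks. The mean is then 15.9 (11 to 20) with a window-based weight, and 16.5 to 17.2 (lower limit 9 to 11 depending on run and stopping pattern, upper 20) with the written weight. Both are close to 16, so the figure does not show which weight was used.

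**Weight of a fully dosed, DLT-free A2 patient.** It is the same for weekly and twice-weekly schedules, since 4/18 = 8/36.

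- Week 4: ½(1 + 4/18) = 0.611
- Week 9: ½(1 + 9/18) = 0.750
- Week 12: ½(1 + 12/18) = 0.833
- Week 18: ½(1 + 18/18) = 1.000
- M6620 stops at week 6: stays at ½(1 + 6/18) = 0.667
- M6620 stops after 4 cycles: stays at 0.833
- 25% reduction from week 5: ½(1 + (4 + 14 × 0.75)/18) = 0.903
- 50% reduction from week 5: ½(1 + (4 + 14 × 0.5)/18) = 0.806

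**Example 1: nobody stops early.** Starts are at weeks 0, 3, 6 and 10. Three patients on schedule 1 are DLT-free, and both weightings put patient 4 on schedule 2. Patient 4 has a DLT before week 13. At week 13 the completed patients have weights ½(1 + 13/18) = 0.861, ½(1 + 10/18) = 0.778 and ½(1 + 7/18) = 0.694. Posterior means for schedules 1/2 are 0.320/0.349 as written: both exceed 0.30, so the next patient gets schedule 1. At full weight they are 0.262/0.291, so the next patient gets schedule 2.

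**Example 2: week 20.** Starts are at weeks 0, 3, 6, 10, 13 and 16, with three patients on schedule 1, three on schedule 2, and one DLT on schedule 2. The ranges cover which schedule 2 patient has the DLT. The posterior mean for schedule 3 is:

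- 0.258 at full weight (recommend 3)
- 0.289 to 0.296 with 18-week dosing (still 3)
- 0.309 to 0.319 if M6620 stops after 4 cycles (recommend 2)

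**Simulation.** 6,000 trials per cell, with the same random numbers for each weighting. The stopping patterns are assumptions, because the documents give no rates.

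| True DLT rates; outcome | Window-based D | Written D, all take 18 weeks | Half stop at week 12 | Thirds stop at weeks 6/12/18 |
|---|---|---|---|---|
| Skeleton; select 4 | 0.52 | 0.51 | 0.44 | 0.37 |
| Skeleton; select 1 | 0.13 | 0.13 | 0.19 | 0.26 |
| Skeleton; safety stop | 1.2% | 2.4% | 2.7% | 3.4% |
| 0.10/0.14/0.18/0.23; select 4 | 0.78 | 0.78 | 0.72 | 0.65 |
| 0.12/0.18/0.26/0.42; select 3 (correct) | 0.31 | 0.29 | 0.27 | 0.27 |
| 0.12/0.18/0.26/0.42; select 4 | 0.42 | 0.46 | 0.40 | 0.31 |
| 0.17/0.26/0.40/0.50; select 3 or 4 (too toxic) | 0.42 | 0.43 | 0.35 | 0.27 |
| 0.17/0.26/0.40/0.50; select 2 (correct) | 0.30 | 0.32 | 0.30 | 0.28 |
| 0.17/0.26/0.40/0.50; select 1 | 0.27 | 0.23 | 0.32 | 0.41 |

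Under the skeleton truth, the paired change in selecting schedule 4 is −0.013, −0.079 and −0.150 for the three written-D columns (SE 0.005 each).

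**The case against.** - **The program may already limit D.** SAP 3.1.1 is a general description, and the Protocol Decision Point Plan, simulation appendix and validated program were not available. This stands as a limit on what is known about implementation. It does not rescue the SAP, whose stated primary model would then be wrong and would still need correcting.
- **The final analysis comes late.** SAP 3.8 places it after 26 weeks of A2 follow-up, when every patient who took all 18 weeks has w = 1. This is correct. The final model is affected only through patients who stop, miss doses or are reduced, but allocations made earlier are affected regardless.
- **The large effects rest on assumed stopping.** True. The documents show that stopping after 4 cycles is foreseeable, not how common it is.
- **The error is cautious.** Also true. When high schedules are toxic, early stopping lowers selection of a too-toxic schedule from 0.42 to 0.27. However, correct selection does not rise (0.30 to 0.28); the trial moves to schedule 1 instead.
- **The examples lie near the 0.30 cut.** They do: Example 1 is one cautious step, and schedule 1 is nowhere near the 0.95 stop.
- **Safeguards exist.** Sensitivity analyses 1 and 3 in SAP 7.4 use time-only weights, and the TMG can overrule the model. This softens the problem. But those analyses use restricted subsets, are specified for dose decision meetings and not for the final MTD, and leave the primary model unchanged. If prescribed dose means the schedule total, a patient stopping after 4 cycles has 12/18 = 67%, below the 75% cut, and drops out of analyses 2 and 3.
- **The weight change was deliberate.** SAP 1.2 records it. Lowering the weight for doses missed inside the window is a reasonable aim; only the A2 denominator is at issue.

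**Conclusion.** The concern holds. As written, an A2 patient with a finished, DLT-free, fully dosed window counts 0.61 at week 4, reaches 1 only at week 18, and stays below 1 if M6620 stops early or is reduced. The weights follow directly from the SAP's definitions and need no assumption beyond the week-5 start taken for the reductions.

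The consequence is overestimated toxicity and under-escalation. Individual allocations can change with full dosing. The effect on final selection is about 0.01 for schedule 4 under the skeleton truth if all take 18 weeks, and 0.08 to 0.15 under the assumed stopping patterns. Those simulated sizes rest on the assumed true rates, uniform DLT onset and stopping patterns. Because this is the primary model for every A2 decision and the correction is cheap, it must be fixed.

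**What to change.** In SAP 3.1.1, define D and v for Stage A2 as the M6620 planned and received within the 4-week DLT window (4 or 8 planned infusions), with v frozen at week 4. A fully dosed DLT-free patient then has w = 0.25, 0.50, 0.75 and 1.00 at weeks 1 to 4. Doses missed inside the window still lower the weight, and later treatment does not affect it.

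State whether prescribed dose in SAP 7.4 means the window or the schedule total. Check which D the program uses. Confirm which weight produced the A2 sample size of 16 (11, 20), and re-run and restate it if it moves.

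The cost is one SAP definition, a small code change and, if needed, a re-run of existing simulations. No patients or visits are added.
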